### 3. Observational Research Protocol

### 3.1. Rationale

Forteo (teriparatide) was initially approved in 2002 in the United States (US) for the treatment of postmenopausal women with osteoporosis at high risk for bone fractures and for increasing bone mass in men with primary or hypogonadal osteoporosis who are at high risk for fracture. In 2009, the treatment indication was expanded to include treatment of men and women with glucocorticoid-induced osteoporosis who are at high risk for fracture.

In rats, in one 2-year (near-lifetime) toxicology study in which doses were administered at levels that produced systemic exposures 3 to 60 times greater than that of a 20- $\mu$ g dose in humans, teriparatide caused increases in bone mass and a dose-dependent increase in the incidence of osteosarcoma, a malignant tumor (Vahle et al. 2002; Forteo USPI 2012). A subsequent rat study conducted to determine the effect of duration of treatment and age at initiation of treatment found that the bone neoplastic response in rats was dependent on both dose and duration of treatment. The study established a "no-effect" dose of 5  $\mu$ g/kg when initiated at 6 months of age, and continued for a duration of either 6 months or 20 months (Vahle et al. 2004). In a long-term study of cynomolgus monkeys (spanning 18 months of treatment plus 3 years of follow-up observation), no bone tumors were detected by radiographic or histological evaluation (Vahle et al. 2008). Studies have shown that the rat skeleton is more sensitive than monkey or human skeletons to the pharmacological effects of parathyroid hormone in the formation of new bone and osteosarcomas (Miller 2008).

Osteosarcoma has rarely been reported in people who have received treatment with Forteo. It is not known if patients who are treated with Forteo have a higher risk of osteosarcoma; however, there have been spontaneous reports of osteosarcoma in Forteo-treated patients.

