# 3.2.2. Secondary Objective(s)

To characterize the Forteo user and comparator cohort using the following:

- Demographic characteristics
- Select prescription drugs dispensed during the baseline period
- Duration of Forteo use for Forteo-treated cohort
- Provider specialty

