### 3.3.2. Data Sources

### IMS Longitudinal Prescription (LRx) Data

The IMS Health (IMS) longitudinal prescription database (LRx) consists of patient-level dispensed prescriptions that enable patient prescription-filling behavior to be tracked across time, payers, and pharmacies. Data contributors include retail chains and independent pharmacies, specialty, mail-order, and long-term care pharmacies. The LRx captures prescriptions purchased through all methods of payment (for example, cash, Medicaid, third party). Currently, the database contains data for over 220 million unique de-identified patients and 1 million physicians. Data are consistently robust across all regions of the country, ranging from 57% coverage in the Southwest to 70% to 80% in the Mid-Atlantic region. The LRx represents >85% of all US retail prescriptions and 40% to 75% of US specialty and mail-order prescriptions (depending on therapeutic area). The IMS documents the saturation of pharmacies in LRx at the state and the Metropolitan Statistical Area (MSA) level; these internal IMS data can be used to estimate data completeness. The LRx data are available from 2005.

The database includes de-identified patient-level longitudinal data such as age, sex, zip codes, dispensed drug (through National Drug Code [NDC]), molecule, form, strength, quantity, and days' supply. All data are Health Insurance Portability and Accountability Act (HIPAA) compliant to protect patient privacy.

There are limitations to using pharmacy claims data for research purposes. Claims data are generated primarily for reimbursement purposes and not research. One such limitation is potential misclassification given that exposure is identified based on a claim for a dispensed prescription without information that confirms whether or not the patient actually used the medication. Based on market research data, 70% of new patients refill their Forteo prescription at least once, and 64% refill their prescription to cover at least 90 days. Therefore, the potential for exposure misclassification is likely to be minimal. In addition, LRx is an open source claims database with data contributed by pharmacies, not health plans. As such, the completeness of data capture is contingent upon the consistency of data contributions from pharmacies.

The patient counts for Forteo from LRx are as follows:

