### 3.3.3.1. Forteo-Treated Patients

Patients treated with Forteo will be identified in the pharmacy claims database using dispensed prescriptions of Forteo identified by NDCs (See Table 2 in Attachment 1). This design improves the accuracy of drug exposure information by eliminating recall bias. One or more dispensed prescriptions of Forteo during the study period will qualify patients as Forteo-exposed. This study design will include both prevalent and new users. If a patient in the comparator cohort receives a prescription for Forteo during the observation period, the person-time will be censored from the comparator cohort on the date of the prescription for Forteo, and subsequent person-time will be counted in the Forteo cohort. Given the limited use of Forteo, this would be expected to rarely occur.

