### 3.3.4. Time Periods

This study will include linkages between commercial pharmacy claims data and state cancer registry data. A linkage is expected to occur late in 2016 or early in 2017 and will include data from 01 January 2005 through December 2 years prior to the linkage year.

An IRR will be estimated assessing osteosarcoma among patients treated with Forteo compared to a general population control group and an osteoporosis-treated control group. Possible differential mortality between the cohorts will be considered in a sensitivity IRR analysis.

The outcome, osteosarcoma, will be identified using 12 identified ICD-O-3 codes in state cancer registry data (See Table 1 in Attachment 1). These codes are currently used for the prospective US Forteo Patient Registry (GHBX [2]).

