### 3.3.4.2. Linkage

The linkage will include a cohort of Forteo users and matched comparators with qualifying dispensed pharmacy claims from 01 January 2005 through December 2 years prior to the linkage year. A deterministic data linkage method will be used to match on demographic variables across the commercial claims study cohorts and cancer registry data. The state cancer registry data will extend through December 2 years prior to the linkage year to account for the 9- to 18-month lag in data collection and reporting among state cancer registries in the year of the linkage. The index date will be the date of the earliest identified dispensed prescription for Forteo and the comparators will have a dispensed prescription during the same calendar month and year.

For optional sensitivity analyses, an attempt will be made to link all study cohorts to the PharMetrics Plus database for ascertainment of medical claims representing baseline patient characteristics. The linkage rate between the LRx database and PharMetrics Plus for this patient population is expected to be very low due to the age distribution of Forteo users and the underrepresentation of the 65 and older patient population.

Analysis will be conducted looking at 2 time periods. The first time period will include all exposure and outcome data from 01 January 2005 through December 2 years prior to the linkage year. This second time period will include a baseline look-back period of at least 3 months prior to the cohort entry date and will include the 6-month lag time. The baseline period will be used to identify descriptive characteristics used for matching for each cohort.

The risk detection window will be the period of time after the index date up until the linkage completion date. Person-time will be calculated for Forteo-treated population and comparator cohorts, and an IRR for the occurrence of osteosarcoma will be calculated to compare the 2 cohorts.

A follow-up linkage, if required, will be a replication of the methods and inclusion/exclusion criteria of the first linkage.

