Descriptive characteristics will be reported for both the Forteo-exposed and comparator cohorts (See Table 1). Among the Forteo cohort, drug utilization patterns will be reported including the number of dispensed prescriptions, mean days of supply, dosage form and strength. Baseline characteristics will be reported in total and stratified by reporting age categories. The number and percent of patients along with descriptive statistics (mean, standard deviation, median, 25th and 75th percentiles) will be reported for continuous data. Categorical variables (for example, payer type) will report the number and percent of patients. Baseline characteristics reported in Table 1 will be summarized for both cohorts.

Two time periods are included with variable look-back windows for assessment of osteosarcoma diagnosis postcohort entry using a data-driven approach. Additionally, 2 comparator cohorts will be established and analyzed. The analysis will be conducted using the following scenarios:

- Primary time period: Using the full 10 years of data available for Forteo exposure and the matched cohort. This will be January 2005 through December 2 years prior to the linkage. State cancer registry data will be linked to all data during this window. This approach assesses all available data and provides a more comprehensive analysis.
- Secondary time period: Using a data-driven approach, a sensitivity analysis will be conducted. This sensitivity analysis will include a variable look-back window where the exposed cohort will only be included when at least a 3-month look-back period is available prior to the index date to describe baseline characteristics.

Findings from these analyses will be described and compared.

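### Forteo use before January 2005 is invisible, so duration of use, cumulative exposure and time since first exposure are left-truncated for prevalent users, and the only partial remedy is conditional

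*Protocol*

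**What the plan says.** All references are to the protocol.

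- **Who enters.** Section 3.3.3.1 counts anyone with one or more Forteo fills in the study period as exposed and adds: "This study design will include both prevalent and new users".
- **When they enter.** Section 3.3.4.2: "The index date will be the date of the earliest identified dispensed prescription for Forteo". Table 1 likewise takes the first observed fill.
- **What can be seen.** Section 3.1 dates US approval to 2002. Section 3.3.2 says of the pharmacy source: "The LRx data are available from 2005". Section 3.3.4 says that the linkage "will include data from 01 January 2005 through December 2 years prior to the linkage year".
- **What is reported.** Section 3.2.2 lists "Duration of Forteo use for Forteo-treated cohort" as a secondary item. Section 3.4.6 refers to cumulative exposure built from claims from index onward.
- **What is removed.** Under Section 3.4.1, a Forteo patient with a registry diagnosis of osteosarcoma before index is dropped together with the matched comparators.
- **The look-back.** In the secondary time period of Section 3.4.1, "the exposed cohort will only be included when at least a 3-month look-back period is available prior to the index date". The stated purpose is to describe baseline characteristics, and Section 3.4 confines those to drugs other than Forteo.

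**The concern.** A patient who started Forteo in 2003 and was still filling in early 2005 receives an index date in early 2005. All earlier treatment is unseen, and nothing in the protocol flags such a patient or reports them separately. Section 3.4.3 lists two sources of exposure misclassification (fills outside coverage or from inconsistent contributors, and drug dispensed but not used). It does not list use before the data begin.

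Two things are at stake. First, Section 3.1 reports that the tumour response in rats depended on dose and duration, so readers will look at the duration figures. Those figures are too short for the patients with the longest time since first exposure. Second, an osteosarcoma diagnosed after true first use but before the first observed fill is not counted as an exposed case. If the registry file shows it, the patient and the matched comparators leave the study.

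LRx is an open source whose completeness depends on the contributing pharmacies (Section 3.3.2). The same gap can therefore arise after 2005 for a patient whose earlier pharmacy was not contributing.

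**Working it through.** **Inputs from the protocol:** approval in 2002, month not given (3.1); data and study window from 01 January 2005 (3.3.2, 3.3.4); linkage late in 2016 or early in 2017, with data to December two years before (3.3.4); 477,140 Forteo patients anticipated (3.4.8).

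**1. The plan's own window.** Section 3.4.1 describes the primary period as "Using the full 10 years of data available for Forteo exposure and the matched cohort".
- Linkage in 2016: 01 Jan 2005 to 31 Dec 2014 = 10.0 years, which agrees.
- Linkage in 2017: to 31 Dec 2015 = 11.0 years.

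**2. Marketed time that cannot be seen.**
- Approval at the end of 2002: 2.0 years before the data start.
- Approval at the start of 2002: 3.0 years.

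**3. Largest understatement of time since first exposure.** Share missed = gap / (window + gap).

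| Window | Gap | True maximum | Recorded maximum | Share missed |
|---|---|---|---|---|
| 10 | 2 | 12 | 10 | 2/12 = 16.7% |
| 10 | 3 | 13 | 10 | 3/13 = 23.1% |
| 11 | 2 | 13 | 11 | 2/13 = 15.4% |
| 11 | 3 | 14 | 11 | 3/14 = 21.4% |

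These are ceilings for the earliest users. Recorded duration and cumulative exposure omit every fill before index, so for left-truncated patients the error can only be downward.

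**4. Average over the whole cohort.** The protocol gives no prevalent share, so this step is assumption only. Average understatement = share × mean unseen time.
- Low: 1% (4,771 of 477,140) × 0.5 years = 0.005 years.
- Middle: 5% (23,857) × 1.0 year = 0.05 years.
- High: 20% (95,428) × 1.5 years = 0.30 years.

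**5. Lag analysis.** Section 3.3.4.1 restarts follow-up 6 months after index. For unseen time u, the real lag is 0.5 + u years: 1.5 years for u = 1 and 3.5 for u = 3. It is never below 6 months.

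**6. Status of the remedy.** Section 3.3.4.2 says that two time periods will be analysed, the second with a look-back of at least 3 months and the 6-month lag. Section 3.4.1 says that the look-back analysis will be done but calls it data-driven. Section 3.4 makes the need for data-driven sensitivity analyses depend on the number of cases and/or a qualitative assessment, and sees little need if there are few or none. For so rare an outcome, that condition could well apply.

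**The case against.** The strongest reply is that this is a declared choice and that the primary result survives it. The IRR compares ever-exposed with unexposed person-time. Prevalent users are truly exposed, and all their counted time follows exposure. That stands, and it limits the point to the descriptive exposure outputs and to cases before index.

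Three stronger readings are tempting, and the protocol does not support them.

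- **Survivor selection biases the primary IRR.** Comparators must also have a fill in the same month and year, and osteosarcoma before index is excluded in both cohorts. Only being still on treatment is specific to Forteo users. No early-period rate is planned, and neither the direction nor the size of any bias is shown.
- **The lag analysis is invalid.** Lags differ between patients, but the 6-month minimum holds for all of them.
- **A dose-response result is distorted.** No IRR by duration is planned, and Section 3.4.4 plans no subgroups. Duration is descriptive.

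A reader might also use the prevalent users' share of person-time as a measure of error. With assumed prevalent shares of 5% and 10%, 10 years of follow-up for them and an assumed 5-year average for new users, that share is 0.5/(0.5 + 4.75) = 9.5% and 1/(1 + 4.5) = 18.2%. None of these inputs is in the protocol, mortality adjustment is ignored, and a share of person-time is not a bias.

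The look-back also deserves credit. Because index is the earliest identified fill, any observed look-back is free of recorded Forteo by construction, and patients first seen in the opening months of 2005 drop out. It works as a short washout. It is still not defined as one, cannot reveal earlier courses and is conditional.

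Finally, a washout length and table labels may sit in an analysis plan that is not at hand. However, the protocol itself fixes the entry rule, the index rule and the conditional status of the look-back.

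**Conclusion.** The point holds for the exposure measures. For patients treated before 2005, duration of use, cumulative exposure and time since first exposure are understated, by at most 2 to 3 years. For the earliest users, that is about 15% to 23% of the true time since first exposure. The direction is certain. The effect across the cohort depends on an unstated prevalent share and may be small: 0.005 to 0.30 years on average over the assumed ranges.

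The loss of cases diagnosed between true first use and the first observed fill follows from the removal rule in Section 3.4.1, but their number cannot be judged from the protocol. No bias of known direction in the primary IRR is established. What needs changing is that the one analysis bearing on the gap is not committed to, and that the limitation is not acknowledged.

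**What to change.** - Keep the all-user primary analysis as it is.
- Turn the look-back analysis in Sections 3.3.4.2 and 3.4.1 into a pre-committed new-user sensitivity IRR that does not depend on the case count. State the Forteo-free period of observed LRx dispensing required before index. Twelve months, giving index dates from January 2006, is one example; the protocol does not determine the length.
- Report how many Forteo patients this excludes.
- Report duration and cumulative exposure for those new users, or label the all-user values as lower bounds.
- Add left truncation of prevalent users to the limitations in Section 3.4.3.

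The cost is one rerun of an analysis already planned, with person-time lost in the sensitivity analysis only. The repair is not complete. A patient treated in 2003 to 2004 who restarts after January 2006 would still count as new, as would one whose earlier fills went to a non-contributing pharmacy.

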### 3.3.3.2. Matched Comparators

Forteo-treated patients will be compared to 2 matched comparator cohorts. The general population control will be included in the main analysis and the osteoporosis population will be included as a sensitivity analysis. The 2 comparator cohorts will be defined as follows:

General population: This group includes patients with a dispensed prescription for any other medication, other than Forteo. For each Forteo user, a target of 4 comparators will be selected. The comparator cohort will be defined as general population pharmaceutical users.

The general population comparator group will be identified as persons with at least 1 dispensed prescription for any product other than Forteo during the same month and year as the identified Forteo user. A target of 4 controls to 1 Forteo-treated patient match is targeted for this group.

Osteoporosis population: This group includes patients with a dispensed prescription, other than Forteo, for treatment of osteoporosis. The osteoporosis comparator group will be identified as persons with at least 1 dispensed prescription for any osteoporosis treatment other than Forteo during the same month and year as the identified Forteo user. A smaller number of available patients are expected in this population and a target of 2 controls to 1 Forteo-treated patient match is targeted for this group.

The comparator cohorts will not have a Forteo prescription filled during the time they contribute as unexposed to Forteo. This group will be matched at baseline to Forteo-treated patients during

the same month as the index period on age group (5-year age categories), sex, geography (zip code), payer type (commercial plans, Medicare, Medicaid, other third parties, and self-pay/cash payments), and count of select unique dispensed prescriptions during the same month/year as Forteo grouped by therapeutic class. Patients will be grouped in 5-year age categories up to age 80, where all patients aged 80 and older will be combined.

At the time of the index date for a patient treated with Forteo, comparators will be eligible to serve as a matched comparator regardless of whether they initiate Forteo in the future.

### 3.3.4. Time Periods

This study will include linkages between commercial pharmacy claims data and state cancer registry data. A linkage is expected to occur late in 2016 or early in 2017 and will include data from 01 January 2005 through December 2 years prior to the linkage year.

An IRR will be estimated assessing osteosarcoma among patients treated with Forteo compared to a general population control group and an osteoporosis-treated control group. Possible differential mortality between the cohorts will be considered in a sensitivity IRR analysis.

The outcome, osteosarcoma, will be identified using 12 identified ICD-O-3 codes in state cancer registry data (See Table 1 in Attachment 1). These codes are currently used for the prospective US Forteo Patient Registry (GHBX [2]).

### 3.3.4.1. Implementing a 6-Month Lag Period

The primary estimate of the IRR (95% CI) assumes that there is no lag time for the induction and latency of osteosarcoma to occur following the index date, which may or may not be biologically plausible. Therefore, a sensitivity analysis of the IRR (95% CI) will be performed, allowing for a 6-month latency period following the index date, if there are enough available patients. For this sensitivity analysis, follow-up time will be recalculated starting at 6 months after the index date rather than starting the day after the index date. This will decrease the amount of persontime in both cohorts and could increase the incidence rates in both cohorts (depending on when cases of osteosarcoma were reported relative to the revised index date), but it should not have as much of an impact on the IRR estimate since the adjustment will be applied to both the Forteo and comparator cohorts.

### 3.3.4.2. Linkage

The linkage will include a cohort of Forteo users and matched comparators with qualifying dispensed pharmacy claims from 01 January 2005 through December 2 years prior to the linkage year. A deterministic data linkage method will be used to match on demographic variables across the commercial claims study cohorts and cancer registry data. The state cancer registry data will extend through December 2 years prior to the linkage year to account for the 9- to 18-month lag in data collection and reporting among state cancer registries in the year of the linkage. The index date will be the date of the earliest identified dispensed prescription for Forteo and the comparators will have a dispensed prescription during the same calendar month and year.

For optional sensitivity analyses, an attempt will be made to link all study cohorts to the PharMetrics Plus database for ascertainment of medical claims representing baseline patient characteristics. The linkage rate between the LRx database and PharMetrics Plus for this patient population is expected to be very low due to the age distribution of Forteo users and the underrepresentation of the 65 and older patient population.

Analysis will be conducted looking at 2 time periods. The first time period will include all exposure and outcome data from 01 January 2005 through December 2 years prior to the linkage year. This second time period will include a baseline look-back period of at least 3 months prior to the cohort entry date and will include the 6-month lag time. The baseline period will be used to identify descriptive characteristics used for matching for each cohort.

The risk detection window will be the period of time after the index date up until the linkage completion date. Person-time will be calculated for Forteo-treated population and comparator cohorts, and an IRR for the occurrence of osteosarcoma will be calculated to compare the 2 cohorts.

A follow-up linkage, if required, will be a replication of the methods and inclusion/exclusion criteria of the first linkage.

